5.3. Lifestyle Considerations

No restrictions are required.

6. STUDY INTERVENTION

6.1. Study Intervention(s) Administered

The term ‘study intervention’ is used throughout the protocol to describe any combination of products received by the participant as per the protocol design. **Study intervention is defined as any investigational treatment(s), marketed product(s), placebo, or medical device(s) intended to be administered to a study participant according to the study protocol.** Study intervention may therefore refer to the individual study interventions or the combination of those study interventions.

Investigational product (IP) in this protocol refers to the investigational study drugs Oral Cabotegravir, Cabotegravir LA, Oral Rilpivirine and Rilpivirine LA. These will be supplied by GlaxoSmithKline/ViiV Healthcare and Janssen Pharmaceuticals, respectively. Commercially available DTG + RPV (Juluca) will be supplied by GlaxoSmithKline/ViiV Healthcare as fixed dose combination tablets.

Participants entering the Long-Term Follow-Up Phase will not have their selected HAART provided as clinical trial material. The selected HAART will be recorded on the Concomitant Antiretroviral Therapy (ConART) eCRF page.

6.1.1. Formulations of CAB + RPV

6.1.1.1. Cabotegravir Tablets (CAB)

CAB is manufactured by GlaxoSmithKline and is formulated as white to almost white oval shaped film coated 30 mg tablets for oral administration, packaged in high density polyethylene (HDPE) bottles with desiccant and child-resistant closure that include an induction seal. CAB tablets will be packaged in bottles of 30 tablets. Participants must keep all IP in its original pack container. GSK will notify sites if and when data are available to support the use of pill boxes. The recommended storage conditions, and expiry date where required, are stated on the product label.

CAB Tablet is composed of cabotegravir sodium, lactose monohydrate, microcrystalline cellulose, hypromellose, sodium starch glycolate, magnesium stearate, and white film-coating. The white film-coating contains hypromellose, titanium dioxide and polyethylene glycol.

6.1.1.2. Rilpivirine Tablets (RPV)

RPV is provided by Janssen Research & Development, LLC, a division of Janssen Pharmaceuticals, as 25 mg tablets that are off-white, round, biconvex, film-coated and debossed on one side with “TMC” and the other side with “25”. RPV is manufactured by Janssen-Cilag S.p.A, Latina, Italy. RPV will be provided as a globally marketed product which includes approvals in the US and the European Union. RPV will be over-labeled and packaged in bottles of 30 tablets. The recommended storage conditions, and expiry date where required, are stated on the product label.

Each tablet contains 27.5 mg of rilpivirine hydrochloride, which is equivalent to 25 mg of RPV. Each tablet also contains the inactive ingredients croscarmellose sodium, lactose monohydrate, magnesium stearate, polysorbate 20, povidone K30 and silicified microcrystalline cellulose. The tablet coating contains hypromellose 2910 6 mPa.s, lactose monohydrate, PEG 3000, titanium dioxide and triacetin.

6.1.1.3. Cabotegravir Injectable Suspension (CAB LA)

CAB LA (GSK1265744 LA) is manufactured by GlaxoSmithKline and is a sterile white to slightly pink suspension containing 200 mg/mL of GSK1265744 as free acid for administration by intramuscular (IM) injection. The product is packaged in a glass vial with a 13 mm gray stopper and aluminum seal. Each vial is for single-dose use containing a withdrawable volume of 2.0 mL (400 mg) or 3 mL (600 mg) and does not require dilution prior to administration. The recommended storage conditions, and expiry date where required, are stated on the product label.

CAB LA is composed of cabotegravir free acid, polysorbate 20, polyethylene glycol 3350, mannitol, and water for injection.

6.1.1.4. Rilpivirine Injectable Suspension (RPV LA)

RPV LA (also named JNJ-16150108-AAA), 300 mg/mL Extended Release Suspension for Injection (G001), is provided by Janssen Research & Development, LLC, a division of Janssen Pharmaceuticals, as a sterile white suspension containing 300 mg/mL of RPV as the free base. The route of administration is by intramuscular (IM) injection. RPV LA is packaged in a single use 4 mL glass vial with a 13 mm grey stopper and aluminum seal. Each vial contains a nominal fill of 2.0 mL (600 mg) or 3.0 mL (900 mg), and does not require dilution prior to administration. The recommended storage conditions, and expiry date where required, are stated on the product label.

RPV LA is composed of RPV free base, poloxamer 338, sodium dihydrogen phosphate monohydrate, citric acid monohydrate, glucose monohydrate, sodium hydroxide, water for injection.

6.1.2. Tablet Formulation of DTG + RPV (Juluca)

Each Juluca tablet contains 50 mg of dolutegravir and 25 mg of rilpivirine, and is a pink, oval, film-coated, biconvex tablet debossed with “SV J3T” on one side. Bottle of 30 tablets with child-resistant closure (contains a desiccant) NDC 49702-242-13.

The recommended storage conditions, and expiry date where required, are stated on the product label.

6.2. Treatment Assignment

Participants transitioning from the LATTE study on oral CAB + RPV treatment will transition to their elected treatment regimen, either Q2M administration of CAB LA + RPV LA or oral DTG + RPV single tablet regimen. Regardless of treatment arm, the

investigator should instruct all participants on the importance of treatment adherence. This study has an open-label design. Dosing is outlined in [Table 2](#).

Table 2 Dosage and Administration

Maintenance Phase (Day 1 to End of Study⁺)	
Q2M Arm- Transitioning from LATTE	
First Injections (Loading Doses) – Day 1 and Month 2	
Day 1	
 • Receive last dose of oral CAB + RPV regimen • Receive CAB LA 600 mg given as 1 X 3 mL IM injection • Receive RPV LA 900 mg given as 1 X 3 mL IM injection
Month 2	
 • Receive CAB LA 600 mg given as 1 X 3 mL IM injection • Receive RPV LA 900 mg given as 1 X 3 mL IM injection
Maintenance Injections – every 2 months (Q2M) following Month 2	
Month 4 to End of Study ⁺ (two 3 mL injections every 2 months)	
 • Receive CAB LA 600 mg given as 1 X 3 mL IM injection • Receive RPV LA 900 mg given as 1 X 3 mL IM injection
Oral DTG + RPV Arm – Transitioning from LATTE	
Day 1 to Month 12 ⁺ (once daily FDC tablet taken with food)	
 • Take one tablet of DTG 50 mg + RPV 25 mg once daily
+Until locally approved and commercially available, the participant no longer derives clinical benefit, the participant meets a protocol-defined reason for discontinuation or until development of CAB LA or RPV LA is terminated	

6.3. Blinding

This will be an open-label study and therefore no blinding is required.

6.4. Packaging and Labeling

The contents of the label will be in accordance with all applicable regulatory requirements.

6.5. Preparation/Handling/Storage/Accountability

- The investigator or designee must confirm appropriate temperature conditions have been maintained during transit for all study intervention received and any discrepancies are reported and resolved before use of the study intervention.
- Only participants enrolled in the study may receive study intervention and only authorized site staff may supply or administer study intervention. All study interventions must be stored in a secure, environmentally controlled, and monitored (manual or automated) area in accordance with the labeled storage conditions with access limited to the investigator and authorized site staff.
- In accordance with local regulatory requirements, the investigator, institution, or the head of the medical institution (where applicable) is responsible for study intervention accountability, reconciliation, and record maintenance (i.e. receipt, reconciliation and final disposition records). The amount of IP dispensed and/or administered to study participants, the amount returned by study participants, and the amount received from and returned to GSK must be documented.
- Further guidance and information for the final disposition of unused study intervention are provided in the Study Reference Manual.
- Under normal conditions of handling and administration, study intervention is not expected to pose significant safety risks to site staff. Take adequate precautions to avoid direct eye or skin contact and the generation of aerosols or mists. In the case of unintentional occupational exposure notify the monitor, Medical Monitor and/or GSK study contact.
- A Material Safety Data Sheet (MSDS)/equivalent document describing occupational hazards and recommended handling precautions either will be provided to the investigator, where this is required by local laws, or is available upon request from GSK.
- Product accountability records must be maintained throughout the course of the study.

IP accountability will be evaluated using pill counts of unused IP for participants receiving oral treatment (oral CAB and oral RPV). This assessment will be conducted each time the participant receives a new (refill) supply of IP through the withdrawal or study completion.

IP accountability for participants receiving CAB LA + RPV LA will be performed at the 'vial' level (e.g., correct number of vials were used for each injection). There may be a small amount of solution remaining in the vial which does not require quantification. Used vials may be discarded at the site once accountability is complete.

No special preparation of study intervention is required for DTG + RPV.

6.5.1. Dosing Considerations for CAB LA + RPV LA

Vials of CAB LA and RPV LA are each supplied as a suspension and need no further dilution or reconstitution. Since RPV LA requires refrigeration, sites should allow the

vial to come to approximately room temperature prior to injecting. The vials should be gently inverted a few times to re-suspend sediments and allow bubbles to subside, and then use a syringe to withdraw the required volume of suspension for IM injection.

All injections must be given intramuscularly in the gluteus medius. Sites may use their discretion as to where in the gluteus muscle each injection is given according to individual participant circumstance. If possible, injections should be spaced approximately 2 cm from one another, from the site of any previous injection or any injection site reaction. The time and location of injection will be captured in the eCRF.

Intermuscular injections should be administered at a 90-degree angle into the gluteus medius muscle using a needle of appropriate gauge and length (In most participants, a 1.5” 23 gauge needle for CAB LA and a 1.5” 23 gauge needle for RPV LA is recommended). The needle should be long enough to reach the muscle mass and prevent study drug from seeping into subcutaneous tissue, but not so long as to involve underlying nerves, blood vessels, or bone. Variable needle lengths and/or needles with different gauge (CAB LA: 21 to 25 gauge; RPV LA: 21 to 23 gauge) are permitted if needed to accommodate individual body types. Longer needle lengths may be required for participants with higher body mass indexes (BMIs, example > 30), to ensure that injections are administered intramuscularly as opposed to subcutaneously. BMI, needle gauge and length used will be collected in the eCRF. Additional details of the injection device used by sites for IM administration including, but not limited to functional performance, may also be collected within the eCRF.

At the Day 1 visit, participants transitioning from oral CAB + RPV should be dosed with the IM regimen within 2 hours of taking the last oral regimen dose where possible.

Should IM maladministration be suspected at any time (e.g., suspected under or overdose or inadvertent IV dosing), the investigator may consider requesting the participant stay onsite for approximately 2-3 hours post dose for safety monitoring and notifying the Medical Monitor. An ECG or any other supportive testing may be obtained at the discretion of the investigator. Additionally, a PK sample may be drawn approximately 2 hours post dosing for future evaluation of CAB and RPV plasma concentrations.

Additional dosing instructions and considerations can be found in the SPM.

6.6. Compliance with Study Intervention Administration

When participants are dosed at the site, they will receive study intervention directly from the investigator or designee, under medical supervision. The date and time of each dose administered in the clinic will be recorded in the participant’s eCRF. The dose of study intervention and study participant identification will be confirmed at the time of dosing by a member of the study site staff other than the person administering the study intervention.

When participants self-administer oral study interventions at home, compliance with CAB + RPV and DTG + RPV dosing will be assessed through querying the participant during the site visits and documented in the source documents and CRF. IP accountability will be evaluated using pill counts of unused IP (CAB, RPV and DTG + RPV tablets). This assessment will be conducted each time the participant receives a new

(refill) supply of oral study medication or any oral bridging phase. A record of the number of CAB, RPV and DTG + RPV tablets dispensed to and taken by each participant must be maintained and reconciled with study intervention and compliance records. Treatment start and stop dates will also be recorded in the eCRF.

Due to the long acting nature of the CAB LA and RPV LA it will be imperative that the participant is compliant with dosing instructions. As part of the screening and participant selection process, it is imperative that Investigators discuss with potential participants the long-term commitments for the trial, and the importance of adhering to treatment regimens. Sites are to have plans in place for adherence counselling for both treatment arms of the study for the duration of the study including the LTFU Phase. In addition, Investigators must have plans in place to perform visit reminders, utilizing participant trackers provided by the study team as needed, and to verify the participant's contact information at each visit. Investigators should contact participants directly in the event that a participant misses any scheduled visit.

6.7. Dose Modifications

No dose reductions, modifications, or changes in the frequency of any components of each regimen will be allowed during the study beyond what is allowed within the protocol or directly approved by the study Medical Monitor. Protocol waivers or exemptions are not allowed. Therefore, adherence to the study design requirements is essential and required for study conduct. See Section 4.4 for the justification of dose.

Supplementary study conduct information not mandated to be present in this protocol is provided in the accompanying Study Procedures Manual (SPM), which is available on the online Study Web Portal. The SPM will provide the site personnel with administrative and detailed technical information.

Please refer to [Appendix 10](#) in Section 12.10 for study management information during the COVID-19 pandemic.

6.7.1. Protocol Permitted Substitutions

6.7.1.1. Oral Bridging

In exceptional circumstances, to address pre-planned missed CAB LA + RPV LA dosing visits, in consultation with the medical monitor, Investigators may provide daily oral CAB 30 mg and RPV 25 mg as a short-term “bridging” strategy for participants who have begun CAB LA + RPV LA. In certain circumstances (e.g., prior to steady state dosing and following a >4 week oral bridge) repeating the loading doses of CAB IM and RPV IM may be required. Should a participant require “oral bridging”, sites must contact the study Medical Monitor for guidance with treatment and dosing strategies prior to a missed CAB LA + RPV LA dose.

Please refer to [Appendix 10](#) in Section 12.10 for study management information during the COVID-19 pandemic.

6.8. Interruption of Study Intervention and Visit/Dosing Windows

IP may be interrupted at the discretion of the Investigator in the event of an AE, according to the severity of the AE.

If one or more antiretroviral medications is held due to toxicity or adverse events, all antiretroviral medications must be held to reduce the risk of development of resistance taking into account both the length of the planned interruption and the pharmacokinetic half-life of each antiretroviral of the regimen, in a way to minimize the risk of development of resistance.

It is important to note that keeping to the participant's visit schedule is a very important component to the study.

Note: All decisions regarding dose interruption / resumption must be discussed with the medical monitor in advance.

6.8.1. IM Dosing

Participants receiving CAB LA and/or RPV LA are anticipated to be at risk for development of virologic resistance if ART is interrupted. The time period during which participants are at risk for development of virologic resistance may be determined by the period between when drug levels fall below therapeutic values and when they fall below levels which exert selective pressure on HIV. This time period will vary by ART agent and is dependent upon effective concentration, inhibitory concentration, and half-life. Plasma concentrations of both LA drugs may be measurable for more than one year following IM injections. Any interruption in IM dosing should be discussed with the Medical Monitor. Investigators should ensure that the participant initiates alternative highly active ART to minimize the risk of developing resistance as concentrations of CAB and RPV decline over time.

IM dosing is expected to occur during the week in which the participant's projected visit falls (as according to the date of the first injection). The first injections for participants from LATTE on oral CAB + RPV will occur at Day 1.

Since the first injection visit (Day 1) will determine the future injection visit schedule for participants, planning for the first injection visit date (within allowed visit windows) should take into consideration the availability of the participants to adhere to future visit windows (planned vacations, business trips, *etc.*).

CAB LA + RPV LA dosing for participants transitioning from oral CAB + RPV is as follows:

All injections should be planned as single injections per drug.

6.8.1.1. IM injections every 2 months (Q2M):

On Day 1, participants will return to the clinic, take the last dose of their oral (CAB 30 mg + RPV 25 mg), and receive the first CAB LA (600 mg) + RPV LA (900 mg) injections (within 2 hours of the final oral dose of CAB + RPV).

The second loading injection will be administered at Month 2 (CAB LA 600 mg + RPV LA 900 mg, with subsequent injections (CAB LA 600 mg + RPV LA 900 mg) occurring every 2 months thereafter. The dosing window for the second injection allows administration between -7 days of the proposed Month 2 injection visit and the proposed Month 2 injection visit date, but preferably not later than the proposed Month 2 injection visit date. After Month 2, a dosing window (± 7 days) for injections is stipulated. The Medical Monitor must be contacted to discuss individual participant case management if a dose has to be administered outside of the window.

6.8.2. Oral Dosing

Any interruption in therapy (scheduling conflicts, life circumstances, *etc.*) during any oral dosing period that is greater than 7 consecutive days must be discussed with the Medical Monitor prior to resumption of therapy. The Medical Monitor must be contacted upon site staff becoming aware of resumption in therapy, if therapy was resumed without prior approval.

Visits for participants in LTFU are expected to occur as projected according to the last injection.

6.9. Treatment of Study Intervention Overdose

For participants receiving Oral CAB, any tablet intake exceeding a total daily dose of 30 mg will be considered an overdose. For participants receiving oral RPV, any dose exceeding a total daily dose of 25 mg will be considered an overdose. For participants receiving DTG + RPV, any tablet intake exceeding the daily number of tablets will be considered an overdose.

For CAB LA and RPV LA, any single dose in excess of the studied doses will be considered an overdose.

Should IM maladministration, specifically overdose or inadvertent IV dosing, be suspected at any time, the participant will stay onsite for approximately 2-3 hours post dose for safety monitoring and an ECG will be performed at 2 hours post dose. The Medical Monitor will be notified in the event of a suspected maladministration.

In the event of suspected maladministration, additional PK samples will be drawn at 2 hours post dosing for evaluation of CAB and RPV concentrations.

For the purposes of this study, an overdose is not an AE (refer to Section 12.4.1) unless it is accompanied by a clinical manifestation associated with the overdose. If the clinical manifestation presents with serious criteria, the event is a SAE (see Section 12.4.2).

If an overdose occurs and is associated with an adverse event requiring action, all study medications must be temporarily discontinued until the adverse event resolves.

The Investigator should use clinical judgement in treating overdose, as ViiV Healthcare is unable to recommend specific treatment.

In the event of an overdose the investigator or treating physician should:

1. Contact the Medical Monitor immediately
2. Closely monitor the participant for adverse events (AEs)/serious adverse events (SAEs) and laboratory abnormalities until the IP can no longer be detected systemically (at least 5 days for oral CAB, oral RPV and DTG + RPV, and 52 weeks for CAB LA and RPV LA)
3. Obtain a plasma sample for pharmacokinetic (PK) analysis if possible within 2 days from the date of the last dose of study intervention if requested by the Medical Monitor (determined on a case-by-case basis).
4. Document the quantity of the excess dose as well as the duration of the overdosing in the CRF.

Decisions regarding dose interruptions or modifications will be made by the investigator in consultation with the Medical Monitor based on the clinical evaluation of the participant.

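### For suspected overdose or inadvertent IV injection, the injection instructions (Protocol 6.5.1) make optional the four steps that Protocol 6.9 requires

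*Protocol*

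**What the plan says.** Protocol Section 6.9 applies when an IM dosing error, limited there to overdose or inadvertent IV dosing, is suspected. It sets four steps, all worded as requirements:

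- Stay and ECG: "the participant will stay onsite for approximately 2-3 hours post dose for safety monitoring and an ECG will be performed", the ECG being timed at 2 hours post dose.
- Notice: "The Medical Monitor will be notified in the event of a suspected maladministration".
- PK: "additional PK samples will be drawn at 2 hours post dosing for evaluation of CAB and RPV concentrations".

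Protocol Section 6.5.1 tells sites how to give the injections. Its trigger is wider but names the same two events: "Should IM maladministration be suspected at any time (e.g., suspected under or overdose or inadvertent IV dosing". All four steps are then permissive:

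- Stay and notice: "the investigator may consider requesting the participant stay onsite for approximately 2-3 hours post dose for safety monitoring and notifying the Medical Monitor".
- ECG: "An ECG or any other supportive testing may be obtained at the discretion of the investigator", with no time given.
- PK: "a PK sample may be drawn approximately 2 hours post dosing for future evaluation of CAB and RPV plasma concentrations".

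Protocol Section 2.3.1 has an accidental-maladministration row for CAB LA and another for RPV LA. Both leave the ECG to the investigator and say that a PK sample may be taken at about 2 hours. Both have the Medical Monitor notified. Neither mentions an onsite stay.

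**The concern.** The two operating sections give different instructions for the same event. Staff with a suspected IV injection in front of them are more likely to be working from the injection section than from the overdose section, and 6.5.1 does not send them to 6.9. A site that follows 6.5.1 exactly could let the participant go without an ECG and would then have departed from 6.9. Sections 6.7 and 8 of the protocol treat adherence to its requirements as essential and rule out waivers, apart from an exception in Section 8 for immediate safety concerns.

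The ECG matters most because it is tied to a time: once the participant has gone home, a 2-hour reading cannot be recovered. The protocol supplies the reason for wanting one. Section 2.3.1 says that accidental IV injection of RPV LA may give higher than expected concentrations soon after the dose. It also reports that oral RPV at 75 mg and 300 mg once daily prolonged QTc in healthy subjects. Table 4 of the SAP lists QTc prolongation at supratherapeutic doses as an adverse event of special interest. For CAB LA, Section 2.3.1 describes the consequences of overdose as unknown.

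**Working it through.** No sample size, power or other computed figure is involved, so the check is a comparison of the texts followed by a count of visits.

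**Step 1: same trigger?** Section 6.9 covers overdose and inadvertent IV dosing. Section 6.5.1 covers those two and underdose. The wider scope explains soft wording for underdose, but not for the two events that both sections name.

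**Step 2: same obligation?**

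| Step | 6.9 | 6.5.1 | 2.3.1 rows |
|---|---|---|---|
| Onsite stay, 2-3 hours | required | optional | not mentioned |
| ECG | required, at 2 hours | optional, no time | optional |
| PK sample, 2 hours | required | optional | optional |
| Medical Monitor notice | required | optional | notified |

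Between 6.9 and 6.5.1, four of four steps differ. On notice, 6.5.1 stands alone: there the verb governing the stay (may consider) also governs notifying the monitor.

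**Step 3: does the text say which prevails?** Neither section cites the other or gives an order of precedence. Section 6.5.1 refers the reader only to the Study Procedures Manual for further dosing instructions.

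**Step 4: would the routine schedule supply the ECG anyway?** Inputs are the Q2M Time and Events Table (8.1.1) and its ECG footnote.

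- Injection visits through Month 26: Day 1 plus Months 2, 4, ..., 26, which is 1 + 13 = 14.
- Injection visits with a scheduled ECG: Day 1 (a 2-hour post-dose ECG for everyone) and Month 12 (after dosing, preferably at 2-4 hours), which is 2.
- Injection visits with none: 14 - 2 = 12.

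The pattern after Month 26 repeats Months 20 to 26, which have no scheduled ECG. The schedule therefore covers the first injection, largely covers Month 12, and covers no other injection visit.

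**Step 5: how often would this arise?** The documents give no expected number of suspected overdoses or IV injections, so no frequency can be attached.

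**The case against.** The best reply is that the two texts can be obeyed together. Optional wording forbids nothing, so a site that follows 6.9 breaches neither section, and 6.9 is the section dedicated to overdose. It requires notice in its text, and its list for overdose again says to contact the Medical Monitor immediately. This holds for a reader who reaches 6.9. It does not help one who stops at 6.5.1, which names the same events and gives no pointer.

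A second reply is that three of the four places (6.5.1 and the two risk rows) leave ECG and PK to the investigator, so discretion may be what the sponsor intended. The documents do not settle that. If so, 6.9 is the text to change, and the inconsistency still needs resolving.

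A third reply is that suspicion may arise at any time, including after the participant has left, when an unconditional stay and 2-hour ECG cannot be met. This is correct and limits the remedy: 6.9 itself needs a timing allowance.

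The Study Procedures Manual and the planned injection training may already give sites a single rule. Neither can be seen here.

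A reader might also infer three stronger things that the documents do not support:

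- **That all four safeguards could be lost at any injection.** Day 1 already has a 2-hour post-dose ECG, Month 12 has a post-dose ECG, and both 2.3.1 rows have the monitor notified.
- **That 6.9 undercuts its own PK step**, because its overdose list asks for a sample "within 2 days from the date of the last dose of study intervention if requested by the Medical Monitor". That item sits in a general list that also covers oral drug and concerns a different time. It does not remove the 2-hour sample.
- **That a QTc hazard from IV RPV LA is established.** The QTc statement concerns repeated oral dosing, and the same entry finds no clinically relevant effect at 25 mg daily. There are no concentration or QTc data after IV RPV LA.

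**Conclusion.** The inconsistency is real and should be corrected. For the same two events, all four steps are required in 6.9 and optional in 6.5.1. The practical exposure is mainly the ECG, at the 12 of 14 injection visits through Month 26 that have none scheduled. The PK step carries little weight, since SAP Section 2.1 says that PK samples would not be analysed. Notice is a drafting fault confined to 6.5.1.

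The size of the risk to participants is unknown, because neither the event frequency nor the effect on QTc is given. This is a safety-conduct matter: the Month 12 Snapshot endpoint and the planned summaries are untouched.

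The conclusion assumes that 6.9 states the sponsor's intended rule and that no document outside the protocol and SAP has already reconciled the two sections.

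**What to change.** - **Section 6.5.1.** State that if overdose or inadvertent IV dosing is suspected, the Medical Monitor will be notified in every case. When suspicion arises while the participant is onsite or can return in time, the 2-3 hour stay, 2-hour ECG and 2-hour PK sample will be done as in 6.9. Otherwise an ECG will be obtained as soon as practicable. Keep investigator discretion on stay, ECG and PK for suspected underdose only.
- **Section 6.9.** Add the same timing allowance, so that late suspicion does not force a protocol deviation.
- **Section 2.3.1.** In the CAB LA and RPV LA maladministration rows, replace the ECG and PK wording with a reference to 6.9.

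The cost is a few sentences in a protocol amendment. For events recognised in time, sites do nothing beyond what 6.9 already asks: an occasional 2-3 hour stay, one ECG and PK sampling. For events recognised late, an ECG when practicable replaces a requirement that could not be met. If the sponsor in fact intended discretion, it should say so in 6.9 and give the reason.
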